### **7.3 Definition of an Overdose for This Protocol and Reporting of Overdose to the Sponsor and Merck**

For purposes of this trial, an overdose of pembrolizumab will be defined as any dose of 1,000 mg or greater ( $\geq 5$  times the indicated dose). No specific information is available on the treatment of overdose of pembrolizumab. Appropriate supportive treatment should be provided if clinically indicated. In the event of overdose, the subject should be observed closely for signs of toxicity. Appropriate supportive treatment should be provided if clinically indicated.

If an adverse event(s) is associated with ("results from") the overdose of a Merck product, the adverse event(s) is reported as a serious adverse event, even if no other seriousness criteria are met.

If a dose of Merck's product meeting the protocol definition of overdose is taken without any associated clinical symptoms or abnormal laboratory results, the overdose is reported as a non-serious Event of Clinical Interest (ECI), using the terminology "accidental or intentional overdose without adverse effect."

All reports of overdose with and without an adverse event must be reported within 24 hours to the Sponsor and within 2 working days hours to Merck Global Safety. (Attn: Worldwide Product Safety; [contact])

#### **7.4 Reporting Pregnancy and Lactation to the Sponsor and to Merck**

Although pregnancy and lactation are not considered adverse events, it is the responsibility of investigators or their designees to report any pregnancy or lactation in a subject (spontaneously reported to them) that occurs during the trial.

Pregnancies and lactations that occur after the consent form is signed but before treatment must be reported by the investigator if they cause the subject to be excluded from the trial, or are the result of a protocol-specified intervention, including but not limited to washout or discontinuation of usual therapy, diet, placebo treatment or a procedure.

Pregnancies and lactations that occur from the time of treatment through 120 days following cessation of Sponsor's product, or 30 days following cessation of treatment if the subject initiates new anticancer therapy, whichever is earlier, must be reported by the investigator. All reported pregnancies should be followed to the completion/termination of the pregnancy. Every effort should be made to report pregnancy outcomes of spontaneous abortion, missed abortion, benign hydatidiform mole, blighted ovum, fetal death, intrauterine death, miscarriage and stillbirth as serious events (Important Medical Events). If the pregnancy continues to term, the outcome (health of infant) should also be reported.

Such events must be reported within 24 hours to the Sponsor and within 2 working days to Merck Global Safety. (Attn: Worldwide Product Safety; [contact])

#### **7.5 Immediate Reporting of Adverse Events to the Sponsor and to Merck**

##### **7.5.1 Serious Adverse Events**

A serious adverse event is any adverse event occurring at any dose or during any use of Merck's product that:

- Results in death
- Is life threatening
- Results in persistent or significant disability/incapacity
- Results in or prolongs an existing inpatient hospitalization

- Is a congenital anomaly/birth defect
- Is another important medical event

*Note: In addition to the above criteria, adverse events meeting either of the below criteria, although not serious per ICH definition, are reportable to the Merck in the same timeframe as SAEs to meet certain local requirements. Therefore, these events are considered serious by Merck for collection purposes.*

- Is a new cancer (that is not a condition of the study)
- Is associated with an overdose.

Refer to Table 7 for additional details regarding each of the above criteria.

For the time period beginning when the consent form is signed until treatment, any serious adverse event, or follow up to a serious adverse event, including death due to any cause other than progression of the cancer under study (reference Section 7.2 for additional details) that occurs to any subject must be reported within 1 business day to the Sponsor and within 2 working days to Merck Global Safety if it causes the subject to be excluded from the trial, or is the result of a protocol-specified intervention, including but not limited to washout or discontinuation of usual therapy, diet, placebo treatment or a procedure.

For the time period beginning at treatment through 90 days following cessation of treatment, or 30 days following cessation of treatment if the subject initiates new anticancer therapy, whichever is earlier, any serious adverse event, or follow up to a serious adverse event, including death due to any cause other than progression of the cancer under study whether or not related to the Merck product, must be reported within 1 business day to the Sponsor and within 2 working days to Merck Global Safety.

Additionally, any serious adverse event, considered by an investigator who is a qualified physician to be related to Merck product that is brought to the attention of the investigator at any time following consent through the end of the specified safety follow-up period (Section 6.3) must be reported immediately to the Sponsor and to Merck Global Safety.

All subjects with serious adverse events must be followed up for outcome.

**SAE reports and any other relevant safety information are to be emailed to the Sponsor, [name], at [REDACTED] and to the Cleveland Clinic SAE inbox at [REDACTED]**

**SAE reports and any other relevant safety information are also to be forwarded to the Merck Global Safety facsimile number: [REDACTED]**

A copy of all 15 Day Reports and Annual Progress Reports is submitted as required by FDA, European Union (EU), Pharmaceutical and Medical Devices agency (PMDA) or other local regulators. Investigators will cross reference this submission according to local regulations to

the Merck Investigational Compound Number (IND, CSA, etc.) at the time of submission. Additionally investigators will submit a copy of these reports to Merck & Co., Inc. (Attn: Worldwide Product Safety; [contact]) at the time of submission to FDA.

### **7.5.2 Events of Clinical Interest**

Selected non-serious and serious adverse events are also known as Events of Clinical Interest (ECI) and must be reported within 24 hours to the Sponsor and within 2 working days to Merck Global Safety. (Attn: Worldwide Product Safety; [contact]).

For the time period beginning when the consent form is signed until treatment, any ECI, or follow up to an ECI, that occurs to any subject must be reported within 24 hours to the Sponsor and within 2 working days to Merck Global Safety if it causes the subject to be excluded from the trial, or is the result of a protocol-specified intervention, including but not limited to washout or discontinuation of usual therapy, diet, placebo treatment or a procedure.

For the time period beginning at treatment through 90 days following cessation of treatment, or 30 days following cessation of treatment if the subject initiates new anticancer therapy, whichever is earlier, any ECI, or follow up to an ECI, whether or not related to Merck product, must be reported within 24 hours to the Sponsor and within 24 hours to Merck Global Safety.

Events of clinical interest for this trial include:

1. An overdose of Merck product, as defined in Section 7.3, that is not associated with clinical symptoms or abnormal laboratory results.
2. An elevated AST or ALT lab value that is greater than or equal to 3X the upper limit of normal and an elevated total bilirubin lab value that is greater than or equal to 2X the upper limit of normal and, at the same time, an alkaline phosphatase lab value that is less than 2X the upper limit of normal, as determined by way of protocol-specified laboratory testing or unscheduled laboratory testing.\*

*\*Note: These criteria are based upon available regulatory guidance documents. The purpose of the criteria is to specify a threshold of abnormal hepatic tests that may require an additional evaluation for an underlying etiology.*

### **7.6 Protocol-Specific Exceptions to Serious Adverse Event Reporting**

Efficacy endpoints as outlined in this section will not be reported to Merck as described in Section 7.5 Immediate Reporting of Adverse Events to the Sponsor and to Merck, unless there is evidence suggesting a causal relationship between the drug and the event. Any such event will be submitted to the Sponsor within 24 hours and to Merck Global Safety within 2 working days either by electronic or paper media.

Specifically, the suspected/actual events covered in this exception include any event that is disease progression of the cancer under study.

The Sponsor will monitor aggregated efficacy endpoint events and safety data to ensure the safety of the subjects in the trial. Any suspected endpoint which upon review is not progression of the cancer under study will be forwarded to Merck Global Safety as a SAE within 2 working days of determination that the event is not progression of the cancer under study

Hospitalization related to convenience (e.g. transportation issues etc.) will not be considered a SAE.

### **7.7 Sponsor Responsibility for Reporting Adverse Events**

All Adverse Events will be reported to regulatory authorities, IRB/IECs and investigators in accordance with all applicable global laws and regulations. Please refer to the Manual of Operations for more details on SAE routing procedures.

**Table 6** Evaluating Adverse Events

An investigator who is a qualified physician, will evaluate all adverse events as to:

V4.0 Grading	CTCAE	Grade 1	Mild; asymptomatic or mild symptoms; clinical or diagnostic observations only; intervention not indicated.
		Grade 2	Moderate; minimal, local or noninvasive intervention indicated; limiting age-appropriate instrumental ADL.
		Grade 3	Severe or medically significant but not immediately life-threatening; hospitalization or prolongation of hospitalization indicated; disabling; limiting self-care ADL.
		Grade 4	Life threatening consequences; urgent intervention indicated.
		Grade 5	Death related to AE
Seriousness	A serious adverse event is any adverse event occurring at any dose or during any use of Merck product that:		
	† Results in death; or		
	† Is life threatening; or places the subject, in the view of the investigator, at immediate risk of death from the event as it occurred (Note: This does not include an adverse event that, had it occurred in a more severe form, might have caused death.); or		
	† Results in a persistent or significant disability/incapacity (substantial disruption of one's ability to conduct normal life functions); or		
	† Results in or prolongs an existing inpatient hospitalization (hospitalization is defined as an inpatient admission, regardless of length of stay, even if the hospitalization is a precautionary measure for continued observation. (Note: Hospitalization for an elective procedure to treat a pre-existing condition that has not worsened is not a serious adverse event. A pre-existing condition is a clinical condition that is diagnosed prior to the use of a Merck product and is documented in the patient's medical history.); or		
	† Is a congenital anomaly/birth defect (in offspring of subject taking the product regardless of time to diagnosis); or		
	Is a new cancer (that is not a condition of the study) (although not serious per ICH definition, is reportable to the Sponsor within 24 hours and to Merck within 2 working days to meet certain local requirements); or		
	Is an overdose (whether accidental or intentional). Any adverse event associated with an overdose is considered a serious adverse event for collection purposes. An overdose that is not associated with an adverse event is considered a non-serious event of clinical interest and must be reported within 24 hours to the Sponsor and to Merck within 2 working days..		
	Other important medical events that may not result in death, not be life threatening, or not require hospitalization may be considered a serious adverse event when, based upon appropriate medical judgment, the event may jeopardize the subject and may require medical or surgical intervention to prevent one of the outcomes listed previously (designated above by a †).		
Duration	Record the start and stop dates of the adverse event. If less than 1 day, indicate the appropriate length of time and units		
Action taken	Did the adverse event cause Merck product to be discontinued?		
Relationship to Merck Product	Did Merck product cause the adverse event? The determination of the likelihood that Merck product caused the adverse event will be provided by an investigator who is a qualified physician. The investigator's signed/dated initials on the source document or worksheet that supports the causality noted on the AE form, ensures that a medically qualified assessment of causality was done.		

CASE 1516

Protocol Amendment 7

06/06/2019

Relationship to Merck Product (continued)	
This initialed document must be retained for the required regulatory time frame. The criteria below are intended as reference guidelines to assist the investigator in assessing the likelihood of a relationship between the test drug and the adverse event based upon the available information.
	
	Exposure	Is there evidence that the subject was actually exposed to Merck product such as: reliable history, acceptable compliance assessment (pill count, diary, etc.), expected pharmacologic effect, or measurement of drug/metabolite in bodily specimen?
	Time Course	Did the AE follow in a reasonable temporal sequence from administration of Merck product? Is the time of onset of the AE compatible with a drug-induced effect (applies to trials with investigational medicinal product)?
	Likely Cause	Is the AE not reasonably explained by another etiology such as underlying disease, other drug(s)/vaccine(s), or other host or environmental factors
The following components are to be used to assess the relationship between the test drug and the AE: (continued)		
	Dechallenge	
Was Merck product discontinued or dose/exposure/frequency reduced?  If yes, did the AE resolve or improve?  If yes, this is a positive dechallenge. If no, this is a negative dechallenge.
 
Note: This criterion is not applicable if: (1) the AE resulted in death or permanent disability; (2) the AE resolved/improved despite continuation of the Sponsor's product; or (3) the trial is a single-dose drug trial); or (4) Sponsor's product(s) is/are only used one time.

	Rechallenge	
Was the subject re-exposed to Merck product in this study?  If yes, did the AE recur or worsen?  If yes, this is a positive rechallenge. If no, this is a negative rechallenge.
 
Note: This criterion is not applicable if: (1) the initial AE resulted in death or permanent disability, or (2) the trial is a single-dose drug trial); or (3) Sponsor's product(s) is/are used only one time
 
Note: if a rechallenge is planned for an adverse event which was serious and which may have been caused by Merck product, or if re-exposure to Merck product poses additional potential significant risk to the subject, then the rechallenge must be approved in advance by the sponsor as per dose modification guidelines in the protocol.

	Consistency with Trial Treatment Profile	Is the clinical/pathological presentation of the AE consistent with previous knowledge regarding Merck product or drug class pharmacology or toxicology?
The assessment of relationship will be reported on the case report forms /worksheets by an investigator who is a qualified physician according to his/her best clinical judgment, including consideration of the above elements.		

## **8 STATISTICAL ANALYSIS PLAN**

The primary goal of the trial is to assess the RECIST-defined tumor response rate outside the radiation field in previously treated NSC lung cancer patients given radiation to an index lesion followed by pembrolizumab. Secondary goals include assessment of toxicity, other efficacy measures such as progression-free survival, response duration, overall survival, and local control of disease within the radiation field, immune response, and biomarkers such as PD-L1 expression.

In previous studies (KEYNOTE 001 and 010) the overall response rate (ORR) to pembrolizumab monotherapy has been approximately 20% in this population. Based on this an underlying ORR in the current trial  $>35\%$  would be considered positive whereas a  $<20\%$  ORR would be considered negative. A two-stage accrual design that allows for early stopping due to lack of efficacy will be employed to test this hypothesis. The maximum accrual goal is 48 eligible and evaluable patients. Initially 29 eligible and evaluable patients will be entered into the trial. If  $<6$  patients respond (observed ORR  $<21\%$ ) the trial will be stopped for (relative) lack of efficacy. If more than 6 patients respond an additional 19 eligible and evaluable patients will be entered. Pembrolizumab plus radiation will be considered effective if overall 12 or more patients respond (ORR  $>25\%$ ). With this design the likelihood of stopping the trial early for lack of efficacy is  $>64\%$  if the underlying ORR is  $<20\%$  and  $<7\%$  if it is  $>35\%$ . The overall type I and II errors are 20% and 10%, respectively.

Safety is an important secondary endpoint. Toxicity will be graded using CTCAE version 4.0 criteria, categorized by organ system, and summarized as frequency counts and percentages. Assuming the trial accrues all 48 patients the risk of a particular type and/or grade of toxicity will be estimable using an exact 90% confidence interval that has a maximum half-width of 13%. The likelihood of observing at least one such event is 86% even if the associated risk is only 5%.

Secondary efficacy endpoints such as progression-free survival, response duration, and overall survival will be summarized using the Kaplan-Meier method. Local control will be summarized as a frequency count and percentage. Other endpoints, such as PD-L1 expression, will be summarized as medians and ranges (e.g. proportion of cells expressing PD-L1) or frequency counts and percentages (e.g. number and percent of patient with PD-L1 expression in  $>50\%$  of cells) as appropriate.

Methods such as Fisher's exact test, chi-square tests, logistic regression (categorical data), the logrank test and proportional hazards models (time to event data) will be used to compare patient groups. These analyses are primarily exploratory and it is acknowledged that they will have relatively low statistical power.

All genomic, transcriptomic, and proteomic molecular analyses will be exploratory. These studies would be analyzed using a prospective-retrospective statistical analysis plan (SAP).

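### The stated 86% chance of seeing at least one toxicity of 5% risk in 48 patients is wrong; it is 91%

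*Combined protocol and SAP*

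**What the plan says.** Section 8 (Statistical Analysis Plan) calls safety an important secondary endpoint and gives two numerical properties for it.

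- **Precision.** "Assuming the trial accrues all 48 patients the risk of a particular type and/or grade of toxicity will be estimable using an exact 90% confidence"; its largest half-width is put at 13%.
- **Detection.** "The likelihood of observing at least one such event is 86% even if the associated risk is only 5" per cent.

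The event in the second sentence is the toxicity of a particular type or grade named in the first, so both sentences share the assumption of 48 patients. Section 1.2.1.4 (Statistics and Sample Size) gives the same two figures in nearly the same words.

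On accrual, Section 8 says "The maximum accrual goal is 48 eligible and evaluable patients" and "Initially 29 eligible and evaluable patients will be entered into the trial". The trial may therefore end with 29 patients if the first stage shows too few responses.

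**The concern.** Both inputs to the detection statement are given, 48 patients and a risk of 5%, and the result follows from one line of binomial arithmetic. That result is not 86%. The sentence before it does reproduce with 48 patients, so the two adjacent safety figures do not follow from one common set of inputs.

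This is the only place where the plan says how likely the trial is to reveal a toxicity of a given frequency. A reader who trusts it would put the chance of missing a 5% toxicity at 14%. A reader who tries to reconstruct it would infer a smaller safety sample, or a lower benchmark risk, than the plan states.

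**Working it through.** **Inputs, all from Section 8 and repeated in Section 1.2.1.4**

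- Number of patients: n = 48, assuming full accrual.
- True risk per patient: p = 5%.
- Threshold: at least one event.
- Stated result: 86%.

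**Step 1. Try to reproduce the stated figure.** With independent patients and a common risk,

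P(at least one event) = 1 − (1 − p)^n = 1 − 0.95^48 = 1 − 0.0853 = 0.9147.

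This is 91.5%, or 91% as a whole number. The gap is 91.5 − 86 = 5.5 percentage points, too large for rounding. The chance of seeing no event is 8.5%, against the 14% implied by the plan.

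**Step 2. Try other readings.**

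| Reading | Result |
|---|---|
| Poisson approximation, 1 − exp(−48 × 0.05) | 90.9% |
| Stage 1 only, 1 − 0.95^29 | 77.4% |
| n = 29 and n = 48 weighted by the early-stopping probability, response rate 20% | 82.4% |
| The same, response rate 35% | 90.4% |
| At least two events in 48 | 69.9% |

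The weighted rows treat toxicity as independent of response. At a 20% response rate the early-stopping probability is 0.643, so the value is 0.643 × 0.774 + 0.357 × 0.915 = 0.824. At 35% the early-stopping probability is 0.074. None of these readings gives 86%.

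**Step 3. Find inputs that would give 86%.**

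- At p = 5%, n = ln(0.14)/ln(0.95) = 38.3. With 38 patients the probability is 85.8%; with 39 it is 86.5%.
- At n = 48, p = 1 − 0.14^(1/48) = 4.0%. Check: 1 − 0.96^48 = 85.9%.

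Neither pair appears in the plan. They are values that fit and do not show where the figure came from.

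**Step 4. Check that 48 is the basis of the paragraph.** The plan gives an "exact 90% confidence interval that has a maximum half-width of 13" per cent. I computed the Clopper-Pearson 90% interval for every possible event count and took half of the widest one:

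- n = 48: 12.6%, which rounds to the stated 13%.
- n = 38: 14.3%, which does not.

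The cruder normal approximation, 1.645 × 0.5/√n, gives 13.3% at n = 38 and 11.9% at n = 48. The plan specifies an exact interval and 48 patients, and on those terms its 13% is right.

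**Step 5. Check the other design figures.** These use the rule in Section 1.2.1.4: 29 then 19 patients, stop at 6 or fewer responses, effective at 12 or more in total.

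| Quantity | Stated | Recomputed |
|---|---|---|
| Early stop at response rate 20% | 64% | 64.3% |
| Early stop at response rate 35% | 7% | 7.4% |
| Type I error | 20% | 19.5% |
| Type II error | 10% | 9.5% |

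All four agree on rounding, so 86% is an isolated wrong number among these design figures.

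**The case against.** No reading of the text rescues 86%. A lost inequality sign is conceivable in Section 8, where some symbols differ from those in Section 1.2.1.4. But Section 1.2.1.4 keeps its signs and still prints a plain 86%. Nor would the number treated fall short of 48 under full accrual: Section 3.3 replaces patients who never start treatment, and any additional treated patients would raise the probability.

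The serious objection is about consequence, and most of it stands:

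- For a fully accrued trial the error is conservative: the plan understates its chance of seeing a 5% toxicity, so nobody is falsely reassured.
- Accrual is set by the response-rate design. Toxicity is summarised by counts and percentages. Neither uses the 86%.
- Safety oversight rests on the dose-limiting toxicity definition (Section 6.5), the hold for safety review based on the first 10 patients (Section 6.5.2) and the termination criteria (Section 3.5). None of these uses the figure either.
- Section 8 largely repeats Section 1.2.1.4 within one combined document, so this is one error printed twice.
- The origin of the figure is unknown. A slip made with the correct inputs is as possible as a calculation from different ones.
- The sentence is conditional on full accrual, so leaving out a figure for an early stop is not itself an error.

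These points limit how much the error matters. They do not make the stated figure correct.

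**Conclusion.** The concern holds. With 48 patients and a 5% risk, the probability of at least one event is 91.5%, and the plan understates it by 5.5 percentage points. This rests only on the plan's own two inputs and on independent patients with a common risk.

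The figure is wrong as written, because it describes a property the design does not have. Its practical weight is small: no sample size, boundary, error rate or analysis changes.

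The direction of the error reverses if the trial stops early. With 29 patients the probability is 77.4%, which is 8.6 points below the printed 86%. By the plan's own figures an early stop has about a 64% chance if the true response rate is 20%.

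**What to change.** In Sections 1.2.1.4 and 8, replace 86% with 91%, keeping the 5% risk and the 48 patients. This is the direct correction, since both inputs are explicit and only the result is wrong. Keeping 86% and changing the risk to 4% would also be arithmetically sound, but it alters the plan's benchmark to preserve a wrong output, so it is the second choice.

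As an optional addition, state that the probability is 77% if the trial stops after 29 patients, so that the statement covers both possible trial sizes.

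The correction costs one number in two places; the addition costs one further clause in each. Neither affects conduct, accrual or analysis.
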